5.3.3 Pembrolizumab-Related Adverse Events

5.3.3.1 General Management of Pembrolizumab-Related Adverse Events

Pembrolizumab related AE management is as per institutional standard of care, with the following recommended guidelines. Pembrolizumab must be withheld for certain drug-related toxicities and severe or life-threatening AEs as per *Table 2*. Subjects should receive appropriate supportive care measures as deemed necessary by the Treating Investigator. Suggested supportive care measures for the management of adverse events with potential immunologic etiology are outlined below. Where appropriate, these guidelines include the use of oral or intravenous treatment with corticosteroids as well as additional anti-inflammatory agents if symptoms do not improve with administration of corticosteroids. Note that several courses of steroid tapering may be necessary as symptoms may worsen when the steroid dose is decreased. These are guidelines and local standard of

care/institutional standards may be followed at the discretion of the Treating Investigator. For each disorder, attempts should be made to rule out other causes such as metastatic disease or bacterial or viral infection, which might require additional supportive care. The treatment guidelines are intended to be applied when the investigator determines the events to be irAEs. For guidelines regarding restarting pembrolizumab, please see *Table 2*.

5.3.3.2 Management of Selected Pembrolizumab-Related Adverse Events

Pneumonitis:

For Grade 2 events pembrolizumab should be held and treatment with corticosteroids initiated. When symptoms improve to Grade 1 or less, steroid taper should be started and continued over no less than 4 weeks. For Grade 3-4 events, immediately treat with intravenous steroids. Administer additional anti-inflammatory measures, as needed. Add prophylactic antibiotics for opportunistic infections in the case of prolonged steroid administration.

Diarrhea/Colitis:

Subjects should be carefully monitored for signs and symptoms of enterocolitis (such as diarrhea, abdominal pain, blood or mucus in stool, with or without fever) and of bowel perforation (such as peritoneal signs and ileus). All subjects who experience diarrhea/colitis should be advised to drink liberal quantities of clear fluids. If sufficient oral fluid intake is not feasible, fluid and electrolytes should be substituted via IV infusion. GI consultation should be considered for Grade 2 or higher diarrhea/colitis. For Grade 2 diarrhea/colitis that persists greater than 3 days despite supportive treatment and anti-diarrheals, pembrolizumab should be held and oral steroids should be administered. For Grade 3 or 4 diarrhea/colitis, pembrolizumab should be held and IV or oral corticosteroids should be administered. For grade 3-4 diarrhea that persists > 4 days despite oral steroids, treat with intravenous steroids followed by high dose oral steroids. If not improving despite IV steroid administration, may also consider additional anti-inflammatory treatments. When symptoms improve to Grade 1 or less, steroid taper should be started and continued over no less than 4 weeks.

New Onset Type 1 diabetes mellitus (including diabetic ketoacidosis [DKA]) or \geq Grade 3 Hyperglycemia, if associated with ketosis (ketonuria) or metabolic acidosis (DKA):

For T1DM or Grade 3-4 Hyperglycemia associated with metabolic acidosis or ketonuria, initiation of insulin is recommended. Pembrolizumab may be held while glucose control is

obtained. Evaluate patients with serum glucose and a metabolic panel, urine ketones, glycosylated hemoglobin, and C-peptide.

Hypophysitis:

For Grade 2 events, hold pembrolizumab, treat with corticosteroids and provide hormonal supplementation as appropriate. When symptoms improve to Grade 1 or less, steroid taper should be started and continued over no less than 4 weeks. For Grade 3-4 events, treat with an initial dose of IV corticosteroids followed by oral corticosteroids. When symptoms improve to Grade 1 or less, steroid taper should be started and continued over no less than 4 weeks. Replacement of appropriate hormones may be required as the steroid dose is tapered.

Hyperthyroidism or Hypothyroidism:

Thyroid disorders can occur at any time during treatment. Monitor patients for changes in thyroid function (at the start of treatment, during treatment, and as indicated based on clinical evaluation) and for clinical signs and symptoms of thyroid disorders. For grade 2-4 hypothyroidism, thyroid hormone replacement therapy is indicated per standard of care. Pembrolizumab may be held if patients are severely symptomatic or show signs of myxedema. For Grade 2 hyperthyroidism, non-selective beta-blockers (e.g. propranolol) are suggested as initial therapy. For Grade 3-4 hyperthyroidism, hold pembrolizumab and consider treatment with corticosteroids in addition to treatment with non-selective beta-blockers. When symptoms improve to Grade 1 or less, steroid taper should be started and continued over no less than 4 weeks. Replacement of appropriate hormones may be required as the steroid dose is tapered.

Hepatitis:

For Grade 2 events, hold pembrolizumab and monitor liver function tests more frequently. Consider treatment with IV or oral corticosteroids if elevation persists for 3-5 days or if there are accompanying clinical symptoms. For Grade 3-4 events, hold pembrolizumab and treat with intravenous corticosteroids for 24 to 48 hours followed by high dose oral steroids. When symptoms improve to Grade 1 or less, a steroid taper should be started and continued over no less than 4 weeks.

Renal Failure or Nephritis:

For Grade 2 events, hold pembrolizumab and administer IV or oral corticosteroids. Consider nephrology consultation. For Grade 3-4 events, treat with IV corticosteroids. When symptoms improve to Grade 1 or less, steroid taper should be started and continued over no less than 4 weeks.

Management of Infusion Reactions:

Signs and symptoms usually develop during or shortly after drug infusion and generally resolve completely within 24 hours of completion of infusion. See *Table 6* below for treatment guidelines for patients who experience a transfusion reaction.

Table 6: Infusion Reaction Treatment Guidelines

NCI CTCAE Grade	Treatment	Premedication at subsequent dosing
Grade 1 Mild reaction; infusion interruption not indicated; intervention not indicated	Increase monitoring of vital signs as medically indicated until the subject is deemed medically stable in the opinion of the investigator.	None
Grade 2 Requires infusion interruption but responds promptly to symptomatic treatment (e.g., antihistamines, NSAIDS, narcotics, IV fluids); prophylactic medications indicated for < =24 hrs	
Stop Infusion and monitor symptoms.
 
Additional appropriate medical therapy may include but is not limited to:
 
 • IV fluids • Antihistamines • NSAIDS • Acetaminophen • Narcotics 
Increase monitoring of vital signs as medically indicated until the subject is deemed medically stable in the opinion of the investigator.
 
If symptoms resolve within one hour of stopping drug infusion, the infusion may be restarted at 50% of the original infusion rate (e.g., from 100 mL/hr to 50 mL/hr). Otherwise dosing will be held until symptoms resolve and the subject should be premedicated for the next scheduled dose.
 
Subjects who develop Grade 2 toxicity despite adequate premedication should be permanently discontinued from further trial treatment administration.
	Subject may be premedicated 1.5h (\pm 30 minutes) prior to infusion of pembrolizumab with: Diphenhydramine 50 mg po (or equivalent dose of antihistamine). Acetaminophen 500-1000 mg po (or equivalent dose of antipyretic).
Grades 3 or 4 Grade 3: Prolonged (i.e., not rapidly responsive to symptomatic medication and/or brief interruption of infusion);	
Stop Infusion.
 
Additional appropriate medical therapy may include but is not limited to:
 
 • IV fluids • Antihistamines 	No subsequent dosing

NCI CTCAE Grade	Treatment	Premedication at subsequent dosing
recurrence of symptoms following initial improvement; hospitalization indicated for other clinical sequelae (e.g., renal impairment, pulmonary infiltrates) Grade 4: Life-threatening; pressor or ventilatory support indicated	
 • NSAIDS • Acetaminophen • Narcotics • Oxygen • Pressors • Corticosteroids • Epinephrine 
Increase monitoring of vital signs as medically indicated until the subject is deemed medically stable in the opinion of the investigator. Hospitalization may be indicated. Subject is permanently discontinued from further trial treatment administration.
	

5.4 Concomitant Therapies

5.4.1 Concomitant Medications

Prior medications (including chronically administered medication) used in the 28 days prior to signing consent will be reviewed and recorded. Patients may continue to use any ongoing medications not prohibited by the inclusion/exclusion criteria or treatment plan.

Comprehensive list of medications to be used with caution or avoided are listed for sitravatinib in Appendix 5.

Anti-diarrheals: In general, patients should be counseled that diarrhea is a possible side effect of the study treatments and advised to take loperamide or a similar medication as needed if diarrhea develops.

Anti-Emetics: Patients may be premedicated for nausea and vomiting.

Medications with QTc Prolonging Activity: The risk of QTc prolongation in patients receiving sitravatinib has not been characterized. Use of medications known to prolong QTc and pose risk of Torsades de Pointes (listed in Appendix 5) should be used with caution.

P-gp and BCRP transporters with Sitravatinib: Sitravatinib is a strong inhibitor of P-gp and BCRP transporters. Concomitant medications that are sensitive substrates or substrates with narrow therapeutic index for these transporters (listed in the Appendix 5) should be used with caution during sitravatinib treatment.

Cytochrome p450 Substrates with Sitravatinib: In vitro experiments in microsomes and recombinant human P450 enzymes suggest that sitravatinib is metabolized by several cytochromes, including CYP1A2, CYP2A6, CYP2B6, CYP2C8, CYP2C9, CYP2D6, CYP2E1, and CYP3A4, with a low risk of any one CYP demonstrating a disproportionate contribution to its metabolism. Caution should therefore be used when administering sitravatinib to subjects taking medications that are strong inhibitors or inducers of the cytochrome P450 system (Appendix 5).

Herbal Medications/Preparations: Herbal medications and preparations should be avoided throughout the study. Herbal medications include but are not limited to the following: St. John's wort, Kava, ephedra (ma huang), gingko biloba, dehydroepiandrosterone (DHEA), yohimbe (yohimbine), saw palmetto, and ginseng.

Immunosuppressive Medications: Use of immunosuppressive medications should be limited to the extent possible to allow testing of the immune-stimulatory mechanisms proposed in this clinical trial. Immunosuppressive medications should be used as needed to manage irAEs and the extent required to manage comorbidities and symptoms of disease.

Anticancer treatments: Use of approved or investigational anticancer treatment is not permitted during the study treatment period, including chemotherapy, bevacizumab/ramucirumab, biological response modifiers, hormone therapy or immunotherapy. No other investigational drug may be used during treatment on this protocol. Concurrent participation in another therapeutic clinical trials is not allowed. Certain ongoing hormonal therapies taken to prevent recurrence of a malignancy not under study (e.g., tamoxifen/aromatase inhibitor for breast cancer) may be permitted after discussion with and agreement of the Sponsor Investigator.

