1.3.2 Sitravatinib Pharmacology

Sitravatinib demonstrated potent, concentration-dependent inhibition of the kinase activity of MET, Axl, MERTK, VEGFR family, PDGFR family, KIT, FLT3, Trk family, RET, DDR2, and selected Eph family members in biochemical assays and inhibited phosphorylation and kinase dependent function in cell-based assays. Sitravatinib also inhibited oncogenic functions associated with target RTKs including MET-dependent cell viability and migration and endothelial tube formation and angiogenesis. Consistent with this anti-tumor and anti-angiogenic mechanism of action, sitravatinib demonstrated anti-tumor efficacy over a broad spectrum of human tumor xenograft models including robust cytoreductive anti-tumor activity in a subset of models exhibiting genetic alterations in RTK targets including MET, RET, FLT3 and others.

In a bidirectional permeability study with Caco-2 cell lines, sitravatinib was classified as a highly permeable compound and not a substrate of P-glycoprotein (P-gp) and breast cancer resistance protein (BCRP). Sitravatinib is an inhibitor of BCRP and P-gp transporters based on in vitro studies.

To assess CYP-mediated metabolism of sitravatinib, phenotyping of sitravatinib in human liver microsome CYPs and recombinant human CYP enzymes was performed. Results suggested that multiple enzymes, including CYP1A2, CYP2A6, CYP2B6, CYP2C8, CYP2C9, CYP2D6, CYP2E1, and CYP3A4, are involved in the metabolism of sitravatinib, with a low risk of any single CYP demonstrating a disproportionate contribution to sitravatinib metabolism.

The potential for sitravatinib to induce expression or activity of selected CYPs was investigated in primary cultures of cryopreserved human hepatocytes (PK-MGCD516-014) and in human liver microsomes (PK-MGCD516-013). For full details, please see the most current version of the Investigator's Brochure. The data overall suggest that sitravatinib is not expected to act as a CYP enzyme inducer at the concentration levels observed clinically. There was little or no evidence of direct inhibition of CYP1A2, CYP2A6, or CYP2E1 by sitravatinib. There was little or no evidence of time- or metabolism-dependent inhibition by sitravatinib of any of the CYP enzymes evaluated. Under the experimental conditions examined, sitravatinib demonstrated direct inhibition of CYP2C8, CYP2C9, CYP2C19, CYP2D6, and CYP3A4/5.

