Based on the FDA Guidance for Industry on In Vitro Drug Interaction Studies — Cytochrome P450 Enzyme- and Transporter-Mediated Drug Interactions (Jan 2020), the calculated ratio of intrinsic clearance values of a probe substrate for an enzymatic pathway in the absence and in the presence of the interacting drug (R1) for reversible inhibition for CYPs 2C8, 2C9, 2C19, 2D6, and 3A4 were equal to or greater than the 1.02 threshold, suggesting a potential for clinical drug interactions.

Preclinical studies suggest elimination of sitravatinib is mainly fecal, with very small (<1%) contribution of urinary excretion.

Using an ultra-centrifugation technique sitravatinib was 98.6% bound to human plasma proteins.

For additional information on sitravatinib pharmacology refer to the most current version of the Investigator's Brochure.

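### Sitravatinib inhibits five CYP enzymes by the protocol's own account, but substrates of four of them (CYP2C8, 2C9, 2C19, 2D6) carry no caution as such in Section 5.4.1 or Appendix 5

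*Combined protocol and SAP*

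**What the plan says.** Section 1.3.2 (Sitravatinib Pharmacology) states that "sitravatinib demonstrated direct inhibition of CYP2C8, CYP2C9, CYP2C19, CYP2D6, and CYP3A4/5". It then reports that the R1 ratios for CYPs "2C8, 2C9, 2C19, 2D6, and 3A4 were equal to or greater than the 1.02 threshold, suggesting a potential for clinical drug interactions". The same section says of the transporters: "Sitravatinib is an inhibitor of BCRP and P-gp transporters based on in vitro studies".

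Section 5.4.1 (Concomitant Medications) turns pharmacology into instructions for sites. It introduces Appendix 5 with the words "Comprehensive list of medications to be used with caution or avoided are listed for sitravatinib in Appendix 5". For P-gp and BCRP it says that co-medications which are "sensitive substrates or substrates with narrow therapeutic index for these transporters (listed in the Appendix 5) should be used with caution". For the CYP enzymes, the paragraph headed as dealing with substrates begins "Cytochrome p450 Substrates with Sitravatinib: In vitro experiments in microsomes and recombinant human P450 enzymes suggest that sitravatinib is metabolized by several cytochromes", adds that this comes "with a low risk of any one CYP demonstrating a disproportionate contribution to its metabolism", and asks for caution in "subjects taking medications that are strong inhibitors or inducers of the cytochrome P450 system (Appendix 5").

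Appendix 5 (Section 12.5) has four headed tables: drugs with known Torsades risk, drugs with conditional Torsades risk, P-gp/BCRP substrates, and CYP3A4 substrates.

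**The concern.** An R1 signal for reversible inhibition describes what sitravatinib may do to a co-medication. The 5.4.1 paragraph addresses what a co-medication may do to sitravatinib. Its heading names one direction and its text gives the other, so the interaction flagged in 1.3.2 never becomes an instruction. Appendix 5 repairs this for 3A4 only.

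The default in 5.4.1 is permissive: ongoing medications may continue unless the eligibility criteria or treatment plan prohibit them. The caution list is therefore the working prompt at medication review. A site told that the list is comprehensive may take a drug's absence as meaning no concern. It could then miss a sensitive or narrow-index substrate of one of the four enzymes whose exposure may rise during daily, continuous sitravatinib dosing.

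A lesser defect sits in the same paragraph. It cites Appendix 5 for strong CYP inhibitors and inducers, and none of the four tables is such a list.

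**Working it through.** No formula applies. The R1 statement cannot be recomputed, because the documents give no inhibition constants, no unbound peak concentrations and no individual R1 values. The check is a side-by-side reading and a count.

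| Flagged in 1.3.2 as inhibited by sitravatinib | Caution sentence for substrates in 5.4.1 | Labelled substrate list in Appendix 5 |
|---|---|---|
| P-gp | Yes | Yes (19 drugs) |
| BCRP | Yes | Yes (8 drugs) |
| CYP3A4 | No | Yes (33 drugs) |
| CYP2C8 | No | No |
| CYP2C9 | No | No |
| CYP2C19 | No | No |
| CYP2D6 | No | No |

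1. CYPs flagged in 1.3.2: 5. With a labelled substrate list: 1. Without: 5 − 1 = 4.
2. Transporters flagged from in vitro data: 2. With both a sentence and a list: 2.
3. The Torsades tables hold 63 and 51 drugs. Their four columns are generic name, brand names, drug class and therapeutic use; none gives an enzyme. Some of these drugs may be substrates of the four CYPs, but the tables do not say so, and 5.4.1 ties them to QTc risk rather than to raised exposure.
4. Appendix 5 tables headed as CYP inhibitors or inducers: 0.
5. Loss in conversion from PDF is an unlikely explanation for the missing rows, because the title of the CYP table itself names only CYP3A4.

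The five CYPs share one stated signal in 1.3.2: direct inhibition, with R1 at or above the same threshold. Nothing in the documents separates 3A4 from the other four.

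**The case against.** The best counter-argument concerns the comparison with the transporters. Section 5.4.1 calls sitravatinib a strong inhibitor of P-gp and BCRP, whereas 1.3.2 says only that the CYP ratios met or exceeded a threshold. The two signals are not described as equal, so a fuller caution for transporters could be deliberate. That stands, and it softens the parity argument. It does not explain why one CYP is listed and four with the same stated signal are not.

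Second, the information is not wholly absent: 1.3.2 names the four enzymes and warns of possible interactions. That is true. What is missing is the operational step, in the places a site consults when reviewing medications.

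Third, other provisions help. Exclusion criterion 8d allows patients on certain antiretrovirals with possible interactions to be excluded, although it refers back to Appendix 5. Sections 1.3.2 and 2.3 refer to the Investigator's Brochure, which is not among the documents and might justify listing 3A4 alone. Medication review at screening and adverse-event checks at each visit continue regardless. None of these, as far as the documents show, is a caution for substrates of the four enzymes, and adverse-event checks act only after harm has begun.

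Finally, no clinical effect is established. That is correct, and it limits the finding to the omission of a prompt.

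**Conclusion.** The concern holds. Four of the five CYP enzymes that the protocol flags have no substrate caution in 5.4.1 and no labelled list in Appendix 5, and the protocol gives no reason. Confidence in the omission is high. The size of its consequence is unknown: neither the strength of any interaction nor the number of affected patients is given.

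The missing item is a prompt for caution, not a prohibition or a dosing rule. The point concerns patient safety and leaves the two-stage ORR design and its analysis untouched. The change should be made, but it does not by itself call for a separate amendment. The inhibitor/inducer reference matters less, because the general caution binds without a list and the protocol sees little risk of a single CYP dominating sitravatinib's metabolism. The mismatch between heading and text suggests an editing slip.

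The conclusion assumes that no site-facing document outside this set, such as the Investigator's Brochure or the Pharmacy Study Manual, already gives the caution. Even if one does, the protocol's claim that its own list is comprehensive would need correcting.

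**What to change.** Add one sentence to 5.4.1 in the form already used for the transporters: caution during sitravatinib treatment with sensitive or narrow-index substrates of CYP2C8, 2C9, 2C19, 2D6 and 3A4. Then either add rows for the four missing enzymes to the Appendix 5 CYP table, or point to a named, maintained source, as Appendix 5 already does for the Torsades lists. The pointer is enough; full drug lists are not essential. If the sponsor judges the four enzymes not to be of concern, one sentence giving the reason would close the point. Correct the inhibitor/inducer reference by adding that list or the same kind of pointer.

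The cost is one or two sentences plus either the added rows (four for substrates and an inhibitor/inducer list) or the pointers. Section 10.2 requires an IRB-approved amendment, and this can be bundled with the next one. Sites would spend slightly longer on medication checks at screening and during treatment.

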5.4.2 Other Concomitant Treatments

5.4.2.1 *Surgery*

The use of surgery to manage cancer lesions during study treatment is discouraged. The impact of sitravatinib on wound healing has not yet been characterized. In the event that major surgery is needed during study treatment, the patient should, if possible, interrupt dosing with sitravatinib 2 weeks in advance of the surgery and resume dosing 2 weeks after the surgery.

5.4.2.2 *Radiation*

Any foreseeable need for palliative radiotherapy should be addressed before study entry if possible and clinically appropriate (e.g., bone lesions at risk for spontaneous fractures or painful lesions). However, these treatments may be used in cases where it is medically necessary or in select cases of oligoprogression at the Sponsor Investigators discretion (see Section 6.8). If radiotherapy is required, sitravatinib should be held the day prior to radiation and resume the day after.

5.4.2.3 *Transfusions*

Patients may receive transfusions as necessary.

5.4.2.4 *Other Anticancer or Experimental Therapy*

Use of approved or investigational anticancer treatment will not be permitted during the study treatment period as discussed in Section 5.4.1. No other investigational drug may be used during treatment on this protocol. Concurrent participation in another therapeutic clinical trial is not allowed.

6 Study Procedures

